To assess the efficiency of data linkage between claims data and credit report data and implications for bias based on proportion of total sample that may not have these data [IR-2], data vendor Optum will link patient addresses to geocoded 2000 and 2010 census data, a process that has previously yielded <1% unlinked data. Information on member race and ethnicity is also included, based on geocodes, US census data, and an imputation strategy incorporating member surname. [MD-2] We will also have detailed benefit information for ~80% of employers, including individual and family deductible levels, HDHP type (HSA, Health Reimbursement Arrangement, or non-account), and copay and coinsurance amount by service type. For employers with missing deductible levels, [MD-2] we have developed an imputation algorithm that has 97.0% sensitivity and 96.2% specificity. To determine employer deductible levels, we will use a benefits type variable that we have for smaller employers (with approximately 100 or fewer employees). For larger employers, we will take advantage of the fact that health insurance claims data are the most accurate source for assessing out-of-pocket obligations among patients who utilize health services. Our claims data contain an in-network/out-of-network deductible payment field. For patients who use expensive or frequent services, the sum of their yearly deductible payments will add up to clearly identifiable exact amounts such as \$500.00, \$1000.00, \$2000.00, etc. When several members have these same amounts, it provides strong evidence that the employer offered such an annual deductible level. It will also be possible to detect employers that offer choices of deductible levels when multiple employees have deductibles at two or more levels, such as 20 employees with an annual amount of \$1000.00 and 12 employees with \$500.00. For employers with at least 10 workers, we therefore will sum each employee's in-network deductible payments and number of claims over the enrollment year and plan to assess other key characteristics such as percentage with Health Savings Accounts. On a randomly selected half of the employer data set that contained our calculated employer characteristics (such as the percentage of patients with deductible levels between \$1000-\$2500) as well as actual deductible amounts, we will use a logistic model that predicts the 3-level outcome of deductible <=\$500/\$500-\$999/>\$1000 based on multiple aggregate employer characteristics such as the first and second most common whole number deductible value, the percentage with Health Savings Accounts or Health Reimbursement Arrangements, the median deductible payment, the percentage of employees using services, the employer size, the percentage of employees with deductible levels between \$100-\$500/ \$500-\$1000/ \$1000-\$2500/ >\$2500, etc. This predictive model will output the probability that employers had deductibles in the three categories (summing to 1) and we will assign the employer to the level that had the highest probability. If we detect employers that had 10 or more employees with whole number deductible levels both above and below \$500 (e.g. \$250.00 and \$1500.00), we will assign the employers' category as "choice." If 100% of employees had Health Savings Accounts, we will overwrite any previous assignment to classify the employer as a high-deductible employer. We will test the predictive model on the other half of the sample for which we have actual deductible levels. At employers with 75-100 workers, we anticipate to find sensitivity and a specificity of over 96%. We will have all study years (2004-2014) available in-house. The sample size (see section C.10) will be sufficient to investigate HDHPs' effects within carefully selected employer groups, as well as within vulnerable patient subgroups.

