
Subgroups [IRQ-4]: We will stratify our analyses by additional characteristics to permit evaluation of vulnerable subgroups: comorbidity level (e.g., highest tertile versus intermediate and lowest tertiles of validated Adjusted Clinical Groups score^{94,95}), SES (e.g., highest versus lowest tertile household income), rural versus urban residency, and race/ethnicity group¹⁵²⁻¹⁵³(non-Hispanic white versus black, Asian, Hispanic, and other). These variables are described in section C.8. For Rural versus non-rural areas; non-rural areas will be the reference group. We will use Rural-Urban Commuting Area (RUCA) codes that reflect travel and shopping patterns at the county level. Using an established probabilistic ZIP code-to-county file,¹⁴⁸ we will assign patients by their residential ZIP codes to RUCA groups. Similar to previous research,¹⁴⁹⁻¹⁵¹ we will categorize the 10-point RUCA classification into: “rural” (RUCA codes 7-10) and “non-rural”, comprising large rural cities/towns (RUCA codes 2-6) and urban areas (RUCA code 1).

C.6 Matching Strategy for Aims 1-3 [CI-5]: For comparing effects among insurance designs, we will use propensity score matching based on both employer- and member-level characteristics to balance the study and control groups on observed characteristics as in our prior work.⁹⁶⁻⁹⁸ We will first match similar employers (to minimize employer selection effects) and then match individuals within groups of similar employers to ensure high comparability between study groups. The individual match will include matching on the baseline outcome measure, an approach crucial to generating estimates comparable to randomized controlled trials.^{77,85}

[name]

We will use the sample selected with this method for interrupted time-series analyses and for pre-post with comparison group difference-in-differences (Section C.9). Use of comparison groups matched at both the employer- and individual-level will increase comparability between HDHP and traditional plan cohorts in baseline employer characteristics, member demographic characteristics, and baseline health care utilization. This offers a further degree of control for any potential contemporaneous changes that may influence specific study outcomes.^{41-44,54,55,80,99}

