(Aim 3) Patient Out-of-Pocket Costs Burden: Analysis of changes in patient costs will rely primarily on a pre-post with propensity-matched comparison group design and a difference-in-differences analytical framework. We will model costs to patients using two-part general linear models. We will select the conditional mean and variance functions based on the actual data, potentially using a log link with a Gamma error distribution.^{127,128} To inform the final model specification, we will employ specification tests including the Pregibon Link test for non-linearity¹²⁹ and a modified Park test to select the conditional variance function.¹²⁷

Stratified Analyses to Assess Effects on Vulnerable Subgroups: We will compare outcomes between HDHP and traditional plan members among strata defined by four covariates: comorbidity burden (e.g., higher versus low tertiles of Adjusted Clinical Groups score,^{81,82} SES (higher versus low tertiles); race/ethnicity (non-Hispanic white versus black, Asian, Hispanic, and other), and rural versus urban residency. We will use GEE or GLMM to express relative changes in outcomes among HDHP member subgroups compared to changes among controls.¹³⁰ If statistical power permits, we will add three-way interaction terms (e.g. study_group*study_period*SES) to assess whether the HDHP switch was associated with a change in baseline disparities in outcomes.

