C.10 Sample Size Estimates and Power Calculations [HT-1 to HT-4]: Using 10 years of data (2003-2012), we found 42 million unique adolescents and adults aged 12-64, approximately 450,000 of whom (~1%) had at least one bipolar disorder diagnosis. This is consistent with our expectation of a lower disease prevalence among commercially-insured adults compared with the 3% prevalence estimated by epidemiological surveys,³ because individuals with bipolar disorder less commonly have private insurance.¹³¹ A total of 109,012 of the 450,000 with a bipolar diagnosis met our inclusion criteria of 2 years continuous enrollment, with the first year in a traditional plan, the second in a traditional or HDHP, and no choice from the employer at any point regarding plan type. Projecting to 2014, our sample will include over 10,800 HDHP members (1525 HSA and 9275 non-HSA) and 43,200 matched traditional plan controls with bipolar illness (1:4 matching). Our smallest HDHP subgroups examined for primary outcomes will include 1525 HSA members (smallest medication adherence cohort) and 2160 non-white members (smallest emergency department and hospitalization outcome cohort).

For interrupted time series analyses of medication adherence, based on assumptions including 12 months of follow-up, autocorrelation of less than 0.3, and 0.05 type I error,¹³² we will have greater than 90% power to detect a 6% relative decrease in adherence in our smallest medication outcome subgroup (HSA-HDHP members). For example, we could detect an adherence rate change from 49% (as seen in previous literature¹³³) to 46% with a standard deviation of 1.5%. This is a *smaller* change in adherence than has been observed previously in HDHP-HSA studies.⁵⁷

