We will use generalized estimating equations to model difference-in-differences analyses of our least frequent outcomes, including emergency department visits and hospitalizations. Based on the smallest subgroup of 2160 non-white HDHP members and their 8640 matched traditional plan controls, a baseline psychiatric hospitalization rate of 10% per year,⁸⁹ (the lowest rate among our measures), 0.05 type I error, 80% power, and a conservative repeated observations correlation assumption of 1, we will be able to detect a 20% relative decrease (e.g., from 10% to 8%). This is smaller than the 27% hospitalization decline we detected in a previous HDHP study.⁵⁴ We will have more power to detect changes for all other outcomes. The power estimates were calculated using PASS software.¹³⁴

C.11 Study Population and Methods for Aim 4 [RQ-3; PC-2]: Ours will be the first qualitative study to explore views of patients with bipolar illness regarding insurance-related barriers to care and experiences with commercial insurance benefits. Qualitative results will complement and inform our quantitative claims-based analyses in Aims 1-3. For Aim 4, DBSA will assist in recruiting **individuals living with bipolar disorder or close family members** to participate in semi-structured telephone interviews. The opportunity to volunteer for participation in interviews will be presented in local DBSA chapter in the form of a flyer for attendees. These flyers will be distributed by DBSA to chapter leadership by means of US mail, email, and routine in-person outreach visits by DBSA officials to chapter meetings. Interested individuals who see the flyer will telephone our co-investigator [name] at DBSA in Chicago. [name] will conduct an initial screening for eligibility, focused on insurance coverage type, English competence, and achieving a rough US geographic balance. [name] will transmit contact details of individual interested in participating to the DPM/HPHCI team. We anticipate identifying ~100 candidate respondents at DBSA, to allow for drop-out due to additional screening, scheduling conflicts, non-consent, etc. In order to achieve full saturation of themes, we anticipate needing 40 completed interviews, as described below. We will schedule more interviews (~60 in total) in order to pilot test our instrument and to account for partial or non-informative interviews.

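### C.10 calls 2160 non-white members the smallest Aim 2 subgroup, but the plan also analyses a 1525-member HSA group in Aim 2, plus rural and possibly separate race strata with no counts given

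*Combined protocol and SAP*

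**What the plan says.** C.10 projects the cohort as follows: "Projecting to 2014, our sample will include over 10,800 HDHP members (1525 HSA and 9275 non-HSA) and 43,200 matched traditional plan controls". It names two smallest subgroups for primary outcomes: 1525 HSA members for medication adherence, and "2160 non-white members (smallest emergency department and hospitalization outcome cohort").

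The Aim 2 power statement rests on the second of these: "Based on the smallest subgroup of 2160 non-white HDHP members and their 8640 matched traditional plan controls". Its other inputs are "a baseline psychiatric hospitalization rate of 10% per year", a 0.05 type I error, 80% power and a repeated-observations correlation of 1. It concludes that a 20% relative decrease, from 10% to 8%, is detectable, and adds that this is smaller than a 27% decline found in a previous HDHP study.

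C.9 says that the analyses in Aims 1-3 first compare all HDHP switchers with traditional-plan members. They then contrast HSA-eligible with HSA-ineligible switchers, each group having its own matched controls. The timeline in Section D repeats the contrast for Aim 2 (months 13-18).

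For the vulnerable subgroups, C.9 lists comorbidity, SES, and "race/ethnicity (non-Hispanic white versus black, Asian, Hispanic, and other), and rural versus urban residency". C.5 gives the same race list and limits rural to RUCA codes 7-10, placing large rural towns in the reference group. C.2, pointing to C.10, says the sample size "will be sufficient to investigate HDHPs' effects within carefully selected employer groups, as well as within vulnerable patient subgroups".

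**The concern.** Calling a group the smallest tells the reader that every other Aim 2 group has at least the stated power. That assurance is wrong for the HSA group, whose size C.10 itself gives. It is unsupported for the rural stratum and for any separate race group, because no counts are given.

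The HSA contrast is one of the study's main questions, and Section D commits to a manuscript on disparities by race/ethnicity, SES, rural residence and comorbidity. With C.2 describing the sample as sufficient within vulnerable subgroups, an imprecise null in a small group could be taken as evidence that the switch had no effect there.

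**Working it through.** **Inputs from C.10.** Control rate p0 = 0.10; HDHP rate p1 = 0.08; n HDHP members and 4n controls; alpha 0.05. The plan does not state sidedness, so two-sided is assumed. The correlation of 1 is read as one effective observation per person.

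**Formulas.** Weighted mean rate: (0.08 + 4 × 0.10)/5 = 0.096.
- SE0 = √[0.096 × 0.904 × (1/n + 1/4n)]
- SE1 = √[0.08 × 0.92/n + 0.10 × 0.90/4n]
- Power, pooled variance: Φ[(0.02 − 1.96 SE0)/SE1]
- Power, unpooled variance: Φ[0.02/SE1 − 1.96]
- Continuity-corrected: as pooled, with ½(1/n + 1/4n) taken off 0.02

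**The plan's own figure, 2160 vs 8640.** SE0 = 0.00709 and SE1 = 0.00667. Pooled: (0.02 − 0.01389)/0.00667 = 0.916, so 82.0%. Unpooled: 1.038, so 85.0%. Continuity-corrected: 80.9%. The stated 80% reproduces.

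**HSA members, 1525 vs 4 × 1525 = 6100.** SE0 = 0.00843 and SE1 = 0.00794. Pooled: (0.02 − 0.01653)/0.00794 = 0.437, so 66.9%. Unpooled: 0.559, so 71.2%. Continuity-corrected: 65.0%. A one-sided pooled test would give 78.0%, still short of 80%.

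**Race groups, if separate.** If black, Asian, Hispanic and other together make up the 2160, the smallest cannot exceed 2160/4 = 540. At most one of the four can exceed 1080, so at least three have 1080 or fewer. At 540 vs 2160, SE0 = 0.01417 and SE1 = 0.01334. Pooled: (0.02 − 0.02778)/0.01334 = −0.583, so 28.0%. Unpooled: 32.2%. Continuity-corrected: 25.1%.

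**Rural.** 2160/10,800 = 20%, so rural is the smaller stratum only below a 20% share. The plan gives no share; 15%, 10% and 5% are assumptions.

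| HDHP n | Group | Power for 10% to 8%: corrected / pooled / unpooled | Decrease detectable with 80% power: pooled / unpooled |
|---|---|---|---|
| 2160 | pooled non-white (C.10) | 80.9 / 82.0 / 85.0% | 19.5 / 18.8% |
| 1620 | rural, if 15% | 67.9 / 69.6 / 73.8% | 22.4 / 21.4% |
| 1525 | HSA (C.10) | 65.0 / 66.9 / 71.2% | 23.1 / 22.0% |
| 1080 | rural, if 10% | 49.1 / 51.5 / 56.4% | 27.2 / 25.7% |
| 540 | rural, if 5%; or ceiling for the smallest of four race groups | 25.1 / 28.0 / 32.2% | 37.6 / 34.8% |

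**Against the 27% benchmark (10% to 7.3%).** The HSA group's detectable decrease of 22-23% is still below 27%, so the reassurance survives there. At 540, power for a 27% decline is only 48-55% (pooled to unpooled), so it does not.

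**Tertiles.** If SES and comorbidity tertiles are cut among HDHP members, each holds about 10,800/3 = 3600, more than 2160.

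**The case against.** **The race wording can mean one pooled group.** The phrase can be read as white versus a combined group listed by its members. The other covariates in that sentence are two-level contrasts, and C.10 itself counts non-white members together. On that reading 2160 is the planned race stratum and the 80% stands. This is a fair objection. A reader might infer that the plan promises 80% power in a race stratum that really has 28-32%. The documents do not support that: 540 appears nowhere in them, it is only a ceiling for the smallest of four separate groups, and C.10 states 80% for no single race category. What remains is an ambiguity, made sharper because C.8 derives the categories separately.

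**The rural shortfall is not demonstrated.** No rural share is given, so the missing count is a reporting gap. That stands.

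**C.10 limits its statement to primary outcomes and lists HSA under adherence.** This does not rescue *smallest*. C.9 and the Section D timeline both carry the HSA contrast into Aim 2, where hospitalization is the outcome.

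**The power levels depend on the test.** An explicit difference-in-differences calculation with within-person correlation 0 / 0.5 / 0.7 gives 53 / 82 / 96% at 2160, 40 / 67 / 87% at 1525 and 17 / 30 / 46% at 540. The levels move, but at any given correlation the smaller group has less power.

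**There is already a caveat.** C.9 says three-way interactions will be added only if power permits. That does not cover the stratified estimates or the HSA contrast.

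**Conclusion.** The concern holds in a limited form. C.10's arithmetic is sound for 2160 vs 8640; what is wrong is the label *smallest*.

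The firm part rests on the documents' own counts. The 1525 HSA members are an Aim 2 group, with about 65-71% power for 10% to 8% and a detectable decrease of about 22-23%, taking a two-sided test and C.10's correlation as read above. These figures are for HSA members against their own controls. Contrasting the HSA effect with the non-HSA effect adds the second estimate's variance, so power for a difference of the same size would be lower still.

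The conditional parts are two. If race groups are analysed separately, the smallest has at most 540 members, power of at most about 25-32% and a detectable decrease of at least about 35-38%, beyond the cited 27%. If rural members are under 20% of HDHP members, that stratum also falls below 2160: about 68-74% power at an assumed 15%, 49-56% at 10% and 25-32% at 5%. The documents do not settle either condition, so neither should be reported as an established shortfall.

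**What to change.** - **C.10:** drop *smallest* for the 2160 group. Give projected HDHP counts and the change detectable with 80% power for each Aim 2 group: HSA, rural, each race group if separate, and the SES and comorbidity tertiles. Keep the 20% claim for the pooled non-white contrast only. State the test and its sidedness.
- **C.5 and C.9:** say that pooled non-white is the powered race contrast, and that the separate groups, if reported, are estimated with confidence intervals.
- **C.2:** qualify the sufficiency sentence so that it matches the revised C.10.

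The cost is wording and a short recalculation from counts obtainable from the claims data. No extra patients are needed. The drawback is that the stated detectable effects become less favourable for HSA and for any small stratum.

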Our study objective is to determine the effects of two types of HDHPs (with and without medications subject to the deductible), compared with traditional commercial insurance, on adolescents and adults with bipolar disorder. To accomplish this, we will conduct quantitative analyses using a very large, geographically diverse dataset of insurer claims complemented by in-depth interviews with individual patients. Insights gained from these interviews, from our Patient/Stakeholder Advisory Panel, and from our ongoing partnership with a major patient advocacy organization (DBSA) will shape and inform the quantitative analyses.

Aims 1-3 will use insurance claims data to examine the impacts of ongoing natural experiments whereby some employers shift their entire employee populations from traditional insurance to HDHPs with two distinct benefit structures. In **Aim 1**, we will evaluate changes in medication adherence, and in the intensity and quality

of other health care following this shift. In **Aim 2**, we will assess changes in adverse events such as preventable psychiatric hospitalizations. In **Aim 3**, we will evaluate changes in patient out-of-pocket cost burden. In each of these first three aims, we will first examine HDHP effects in the overall population of patients with bipolar illness, then compare differences in effects between the two types of HDHPs, and finally examine changes in specific vulnerable subgroups, including racial/ethnic minorities, poorer patients, rural patients, and patients who have high comorbidity burdens. In **Aim 4**, using interviews, we will explore patient experiences coping with complex insurance benefits and gather their views on higher- and lower-value care, contrasting these to standard definitions and conceptions of healthcare “value.”

Throughout the three years of study, we will rely on our Patient/Stakeholder Advisory Panel and our investigative partnership with DBSA to monitor our progress, to continuously bring in fresh community perspectives on our work and its relevance, and to help us refine our study approach.

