C.9 Analysis Plan for Aims 1-3 [IR-3; HT-1 to HT-4]: Overview: These analyses will determine how specific outcomes change after employer-mandated switching from traditional plans to HDHPs. To address methodological standard IR-3, we plan to use the most rigorous quasi-experimental retrospective longitudinal designs and analyses available for AIMS 1-3, namely interrupted time series with comparison series matched on multiple baseline covariates as well as the baseline trend of outcome measures. For Aim 4 we will use appropriate standard techniques for qualitative analyses of interview data (detailed below). We will first compare the characteristics of our matched cohorts (HSA-eligible and HSA-ineligible HDHP members, and traditional plan controls) using chi-square tests, t-tests and Poisson or quantile regression.¹²⁶ We will contrast sociodemographic characteristics, employer characteristics, and baseline health care utilization. Subsequent analyses will use time-series plots and rigorous analytical methods appropriate for each outcome, described below. Data collected on the same individuals in successive years are correlated (“repeated observations”). The extended general linear models—generalized estimating equations (GEE) and generalized linear mixed models (GLMM) for binary, count, or continuous measured outcomes—are appropriate methods for estimating parameters to adjust for these correlations within subjects.^{82,83} The term of interest in our GEE or GLMM models will be the interaction between *time* (pre versus post) and *cohort* (HDHP versus traditional plan). Statistical analyses in Aims 1-3 will first compare those transitioning to HDHPs with patients remaining in traditional plans; then contrast effects between HDHP members with full drug cost-sharing (HSA-eligible plans) and those transitioning to HDHPs without full drug cost-sharing (HSA-ineligible HDHPs). Each HDHP group will have as controls only those traditional plan members paired to a given HDHP member during the propensity score match. To examine possible selection effects due to applying our enrollment criteria and propensity matching approaches (see C.10), we will also compare our analytic population to members with bipolar disorder who were excluded from the sample.^[MD-4; CI-2]

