(Aim 1) Access to Appropriate Outpatient Care: We will assess changes before and after the index month in the *utilization and adherence* outcomes listed in C.7 for Aim 1 using patient-level *interrupted time series with comparison series*. The interrupted time series design includes multiple observations over time both before and after an intervention (i.e., the plan switch) and adjusts for most threats to internal validity (e.g., secular changes in prescribing, aging of the population) because it adjusts for baseline trends in study outcomes that are unrelated to the intervention.⁸⁰ Furthermore, our strategy of matching on the baseline outcome trend should generate highly robust causal estimates. We will use patient-level segmented linear regression models^{58,84} to statistically estimate patient-level changes in both level and trend in outcomes after the switch to HDHPs, while controlling for autocorrelation of the data and individual-level covariates. The segmented regression models include a constant term; an integer variable indicating *time* in months (t) from the start of the observation period to estimate baseline trend; a binary variable, *intervention*, indicating the period after the index month, to estimate change in level; and an interaction between *intervention* and *time*, to estimate change in trend. We will test the statistical significance of level or trend changes, adjusting for first-order autocorrelation between sequential monthly measurements using the empirical sandwich estimator in GEE.⁵⁸

For selected quality measures (i.e., likelihood of a quarterly outpatient mental health visit or receiving

guideline-recommended lab monitoring when using lithium, valproate, carbamazepine, and 2nd generation antipsychotics; C.7), our approach will be a pre-post with comparison group and difference-in-differences design. Logistic regression models will assess the independent effect of HDHPs on these outcomes, while controlling for patient-level covariates and secular utilization trends (by including index month).^{54,55,99}

(Aim 2) Adverse Patient Clinical Outcomes: To examine the impact of transitioning to HDHPs on changes in rates or risk of psychiatric/non-psychiatric ED visits and hospitalizations, we will use a pre-post with comparison group difference-in-differences design. We will control for patient-level covariates in the models. We will use GLMM to model the effect of HDHPs on annual hospitalization days.

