Aim 4. Pilot test and refine interview procedures and guide. Recruit 75% of interview respondents. Complete 50% of interviews. Ongoing transcription and create coding scheme for interview analysis.

Months 13-18 Additional refinement of protocols with Advisory Panel input and DBSA community feedback.

Aims 1-3. Finalize Aim 1 main analyses and draft **manuscripts 1 and 2** reporting changes in access to appropriate outpatient treatment and quality of care. Additional dissemination activities. Preliminary Aim 2 analyses of changes in adverse patient outcomes (psychiatric/non-psychiatric ED visits and hospitalizations) following switching to HDHPs. Contrast HDHP members with and without full drug cost-sharing. Early dissemination of Aim 2 results through conference abstract submissions, additional stakeholder meetings, and DBSA avenues of communication.

Aim 4. Refine coding for interview analysis. Completion of remaining interviews, attaining theme saturation. Ongoing transcription and analysis of interviews. Early dissemination of interview findings through conference submissions, stakeholder meetings, and DBSA avenues of communication.

Months 19-24 Additional refinement of protocols with Advisory Panel input and DBSA community feedback.

Aims 1-3. Finalize Aim 2 main analyses and draft **manuscript 3** reporting changes in adverse patient outcomes (psychiatric/non-psychiatric ED visits and hospitalizations) following switching to HDHPs. Additional dissemination activities from Aim 2. Preliminary Aim 3 analyses of changes in patient out-of-cost burden. Stratify analyses contrasting HDHP members with and without full drug cost-sharing. Early dissemination of Aim 3 results through conference abstract submissions, additional stakeholder meetings, DBSA avenues of communication.

Aim 4. Finalize analyses of interviews and draft **manuscript 4** on patient perspectives on access to

appropriate treatment of bipolar in the context of commercial plans. Dissemination of results.

Months Additional refinement of protocols with Advisory Panel input and DBSA community feedback.

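### The correlation of 1 that C.10 calls conservative is the most favourable value for the planned difference-in-differences, and the smaller HSA cohort has no hospitalization power figure

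*Combined protocol and SAP*

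**What the plan says.** C.9 (Overview) sets the estimand for Aims 1-3: "The term of interest in our GEE or GLMM models will be the interaction between" time (pre versus post) and cohort (HDHP versus traditional plan). C.9 (Aim 2) applies this to "psychiatric/non-psychiatric ED visits and hospitalizations, we will use a pre-post with comparison group difference-in-differences design". C.4 gives each member one year before and one year after the switch.

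C.10 sets out the power for these outcomes. The inputs are 2160 non-white HDHP members, 8640 matched controls, a psychiatric hospitalization rate of 10% per year, type I error 0.05 and 80% power. It then says that with "a conservative repeated observations correlation assumption of 1, we will be able to detect a 20% relative decrease", for example from 10% to 8%, and notes that this is smaller than a 27% decline found in an earlier HDHP study.

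C.10 names its smallest groups as "1525 HSA members (smallest medication adherence cohort) and 2160 non-white members (smallest emergency department and hospitalization outcome cohort". Yet section C says that in each of Aims 1-3 the team will "then compare differences in effects between the two types of HDHPs, and finally examine changes in specific vulnerable subgroups". C.9 says it will "then contrast effects between HDHP members with full drug cost-sharing (HSA-eligible plans" and members of HSA-ineligible plans, and the section D milestones for months 13-18 list, within the Aim 2 work, "Contrast HDHP members with and without full drug cost-sharing. Early dissemination of Aim 2 results".

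**The concern.** A high correlation between repeated observations is the cautious assumption only when the observations are averaged over time, because a second correlated year then adds little information. A difference-in-differences subtracts one year from the other, so a high correlation removes person-to-person variation and shrinks the standard error. The label in C.10 therefore points the wrong way for the test that C.9 plans, and the 20% figure appears to belong to a different comparison.

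C.10 is the plan's only statement of what Aim 2 can detect in its small groups. If it is too favourable, a null result in non-white or HSA members could be read as adequately powered when it was not. The HSA group matters separately: it is one arm of the benefit-design contrast, it is smaller than the group C.10 uses, and it has no power figure for hospitalization or ED visits.

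**Working it through.** **Inputs.** From C.10: 2160 HDHP members and 8640 controls; 1525 HSA members, hence 4 × 1525 = 6100 controls at the stated 1:4 ratio; 10% baseline; target 8%; type I error 0.05. From C.4: two annual periods. Assumptions of this review: a two-sided test, controls at 10% in both years, and a range of rho, since the documents give none.

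**1. Reproduce the 20%.** With m = 2 observations, the time-averaged variance factor is (1 + (m − 1)rho)/m, which equals 1 at rho = 1. That reduces the calculation to a single-period comparison of 8% with 10%.

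- Unpooled SE = sqrt(0.08 × 0.92/2160 + 0.10 × 0.90/8640) = 0.00667. Power = Φ(0.02/0.00667 − 1.96) = 85%.
- Pooled: the common rate is (0.08 + 4 × 0.10)/5 = 0.096, null SE 0.00709. Power = Φ((0.02 − 1.96 × 0.00709)/0.00667) = 82%. The detectable decrease at 80% power is 19.5%.

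The stated figure is recovered as a post-period comparison. The PASS procedure is not named, so this identification is inference.

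**2. Power for the planned interaction.** For each group,

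Var(change) = [p0q0 + p1q1 − 2·rho·sqrt(p0q0·p1q1)]/n.

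The two group variances are added, and power = Φ(0.02/SE − 1.96). For 2160 vs 8640 at rho 0: SE = sqrt((0.0900 + 0.0736)/2160 + 0.1800/8640) = 0.00983, and power = Φ(0.07) = 53%.

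| rho | SE, 2160 vs 8640 | Power | Detectable decrease | SE, 1525 vs 6100 | Power | Detectable decrease |
|---|---|---|---|---|---|---|
| 0 | 0.00983 | 53% | 27.1% | 0.01170 | 40% | 32.0% |
| 0.2 | 0.00879 | 62% | 24.4% | 0.01047 | 48% | 28.8% |
| 0.4 | 0.00762 | 75% | 21.3% | 0.00907 | 60% | 25.2% |
| 0.5 | 0.00696 | 82% | 19.5% | 0.00829 | 68% | 23.1% |

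Power is for 10% to 8%; detectable decreases are relative, at 80% power. Solving for 80% power gives rho = 0.47 for non-white members (0.46 to 0.51 across log-odds and null-variance forms) and 0.63 for HSA members (0.62 to 0.65). A simulated logistic difference-in-differences with patient-clustered standard errors (40,000 runs) gave similar power at rho 0, 0.2, 0.4 and 0.5: 54%, 64%, 77% and 84% for 2160; 42%, 50%, 61% and 69% for 1525.

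Power rises throughout with rho. A correlation of 1 cannot in fact occur between binary outcomes at 10% and 8%; the maximum is about 0.88.

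**3. HSA members in the single-period calculation.** Repeating step 1 with 1525 vs 6100 gives 67% pooled and 71% unpooled, with a detectable decrease of 23.1% (pooled). The shortfall for 20% therefore remains even in the calculation the sponsor appears to have used.

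**4. Overall comparison.** With 10,800 vs 43,200, SE at rho 0 is 0.00439 and power exceeds 99%.

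**The case against.** The strongest defence is the matching. C.6 says: "The individual match will include matching on the baseline outcome measure". If baseline balance is close and the analysis uses it, the relevant variance is nearer the post-period variance times (1 − rho²). Over rho 0 to 0.5 that gives 85% to 93% power for non-white members, with no minimum correlation, and 71% to 83% for HSA members, reaching 80% only from about 0.44. This stands as a possibility, and it makes the 0.47 threshold conditional on an unadjusted variance. It does not rescue the text: C.10 invokes no such variance, propensity matching does not guarantee exact balance on the baseline outcome, and an interaction test with patient-clustered standard errors does not capture the gain by itself. Under this form too, higher rho means more power.

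The second defence is the 27% benchmark. For a 27% decrease (10% to 7.3%), unadjusted power in non-white members is 79.6% at rho 0 and reaches 80% at about 0.01, so adequacy against that effect largely survives. HSA members need rho of about 0.30, although a single-period comparison gives 92% to 94%. This limits the consequence for the group C.10 chose, but the plan's claim is 20%, not 27%.

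It is also fair to say that the 20% is not a slip in calculation. It is a sound figure for a comparison other than the planned one. The cohort sizes are projections to 2014, so the thresholds should be read as approximate.

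**Conclusion.** The concern holds. For the pre/post-by-cohort interaction, calling a correlation of 1 conservative is backwards. The claim of 20% at 80% power in non-white members rests on an unstated correlation of about 0.47 or more, or on a baseline-adjusted variance that the plan does not state. Over rho 0 to 0.5 the unadjusted power is 53% to 82%.

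C.10 also misnames the smallest hospitalization cohort. The 1525 HSA members are fewer than 2160, are analysed for Aim 2, and have unadjusted power of 40% to 68% for a 20% decrease. These are figures against their own matched controls; the HSA versus non-HSA contrast also carries the non-HSA group's sampling error.

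The results assume a two-sided 0.05 test, flat 10% control rates and 1:4 matching. The true year-to-year correlation is unknown, so whether power is actually below 80% cannot be settled from the documents. The direction of the error and the missing HSA figure do not depend on it. The overall HDHP comparison is not affected.

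**What to change.** In C.10:

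- Remove the word conservative, and state an assumed pre-post correlation with its source.
- Report power or detectable decrease for the period-by-cohort interaction over an explicit range, for example rho 0 to 0.5, for both the 2160 non-white and the 1525 HSA members.
- If power is meant to rest on baseline matching or adjustment, say so, give that variance, and specify the analysis that realises it.
- Correct the statement that non-white members are the smallest ED and hospitalization cohort.

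The cost is restated power text, with less favourable figures for the small groups. No members, data or analyses are added.
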